**Table 1**

|            | Dose level 0   | Dose level -1   | Dose level -2  |
|------------|-----------------------|------------------------|-----------------------|
| E7070      | 400 mg/m  | 25% reduction          | 50% reduction         |
| Cytarabine | 1 gm/m    | 0.75 gm/m  | 0.5 gm/m  |
| Idarubicin | 8 mg/m    | 6 mg/m     | 4 mg/m    |

**V. PATIENT ELIGIBILITY:**

**INCLUSION:**

1. All patients with histologically or cytologically confirmed relapsed or refractory AML [except acute promyelocytic leukemia], or HRMDS (Int-2 high risk by IPSS or >10% blasts in marrow).
2. Patients must be 18 years or older.
3. Patients must have a performance status of 0-2 (Zubrod scale).
4. Patients must have adequate renal function (serum creatinine ≤ 1.3 mg/dL and/or creatinine clearance > 40 mL/min). Patients with renal dysfunction due to organ infiltration by disease may be eligible after discussion with the P.I., (up to creatinine ≤ 2.0) and appropriate dose adjustments will be considered.
5. Patients must have adequate hepatic function (bilirubin ≤ 2.0 mg/dl; SGOT or SGPT ≤ 3X the ULN for the reference lab unless due to leukemia or congenital hemolytic disorder or bilirubin). Patients with hepatic dysfunction (SGOT/SGPT up to ≤ 5X ULN) due to organ infiltration by disease may be eligible after discussion with the P.I., and appropriate dose adjustments will be considered.
6. Patients must have normal cardiac ejection fraction.
7. QTc interval ≤ 480 msec.

8. Patients must sign an informed consent form indicating that they are aware of the investigational nature of this study, in keeping with the policies of the hospital.
9. Female patients must not be pregnant or lactating. Female patients of childbearing potential (including those <1 year post-menopausal) and male patients must agree to use contraception.

**EXCLUSION:**

1. Patients must not have untreated or uncontrolled life-threatening infection.
2. Patients must not have received chemotherapy and/or radiation therapy within 2 weeks. Hydroxyurea is allowed up to 48 hours prior to starting therapy in the setting of rapidly proliferating disease. (For details of allowance of hydroxyurea use after the start of study drug please refer to section VI)
3. Patients must not have received an investigational anti-cancer drug within two weeks of E7070 administration.
4. Any other medical condition, including mental illness or substance abuse, deemed by the Investigator to be likely to interfere with a patient's ability to sign informed consent or cooperate and participate in the study or with the interpretation of the results.

**VI. CONCOMITANT MEDICATIONS:**

Use of hydroxyurea to control proliferative disease will be allowed starting from day 2 until day 7 Cycle 1. Maximum dose of hydroxyurea allowed daily is 5 gram and hydroxyurea must be discontinued once administration of idarubicin and cytarabine is started.

**VII PRETREATMENT EVALUATION (within 7 days of start of study drug except where noted)**

- History and Physical Examination to include vital signs and weight.
- CBC with differential platelets, glucose, total protein, albumin, electrolytes [sodium, potassium, chloride, CO2], calcium, phosphorus, magnesium, uric acid, bilirubin (total, direct), SGPT (ALT) or SGOT (AST), alkaline phosphatase, lactate dehydrogenase, creatinine, blood urea nitrogen.
- Record all concomitant medications and baseline adverse events.
- Bone marrow aspirate and/or biopsy (within one month), and cytogenetics, unless these tests were done within 3 months.
- Chest x-ray (PA and lateral) [at or within one month of screening].
- Electrocardiogram [at or within 1 month of screening].
- Evaluation of cardiac ejection fraction (MUGA or ECHO) (at or within 1 month of screening).

- Urine or blood pregnancy test for women of childbearing potential (within 7 days prior to day 1).
- ECOG assessment.

## **VIII. EVALUATION DURING STUDY**

- CBC, differential (if WBC >  $10^9/L$ ), every 4-7 days during Cycle 1 and every 1 to 4 weeks during Cycle 2.
- Record all concomitant medications and adverse events: continuously during study.
- Disease assessment: Cycle 1, Day 28 (+/- 3 days)
- Electrocardiogram on Day 2 (+/- 1 day) and Day 8 (+/- 2 days) of Cycle 1 done at least 1 hour after completion of E7070 infusion.
- Bone marrow aspiration on day 28 (+/- 3 days) and as indicated at the discretion of the treating physician until documentation of response. Bone marrow examinations may be omitted in patients where there is clear evidence of active disease (e.g., increasing blasts in peripheral blood).
- Creatinine, total bilirubin, electrolytes, AST and/or ALT once every week during induction Cycle 1, then every 2-4 weeks during Cycle 2.
- Safety lab assessments (CBC, differential, platelets, creatinine, total bilirubin, electrolytes, AST and/or ALT) can be performed by local physician, see Section X.

## **IX. END-OF-TREATMENT VISIT (30 days [+/- 5 days] after the last dose of study drug), unless the patient has started on alternative therapy**

- CBC, platelet count, differential
- Serum chemistries (creatinine, total bilirubin, electrolytes, AST and/or ALT)
- Record adverse events

## **X. LONG TERM FOLLOW-UP (unless the patient has started on alternative therapy)**

Patients will have blood counts and chemistry studies every 2-3 months for up to 2 years. These can be done by a local physician. If the counts are abnormal and relapse is suspected, patients will return to M. D. Anderson for additional evaluation of their disease. See Section X.

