|  | 
keeping with the policies of the hospital.
 
9. Female patients must not be pregnant or lactating. Female patients of childbearing potential (including those <1 year post-menopausal) and male patients must agree to use contraception.
 
Exclusion:
 
 
1. Patients must not have untreated or uncontrolled life-threatening infection.
 
2. Patients must not have received chemotherapy and/or radiation therapy within 2 weeks. Hydroxyurea is allowed up to 48 hours prior to starting therapy in the setting of rapidly proliferating disease. For details of allowance of hydroxyurea use after the start of study drug, please refer to section VI.
 
3. Patients must not have received an investigational anti-cancer drug within two weeks of E7070 administration.
 
4. Any other medical condition, including mental illness or substance abuse, deemed by the Investigator to be likely to interfere with a patient's ability to sign informed consent or cooperate and participate in the study or with the interpretation of the results.
 
 |
| TOTAL EXPECTED NUMBER OF PATIENTS | Up to 40  |
| STUDY DRUGS                       | 
E7070
 
Idarubicin
 
Cytarabine
 
Dexamethasone
   |
| ROUTE OF ADMINISTRATION           | IV  |
| DOSE REGIMEN                      | 
E7070 400 mg/m^2 intravenously (IV) approximately over 1 hour on day 1 and day 8:
 
Idarubicin 8 mg/m^2 IV approximately over 1 hour daily x 3 (days 9-11)
 
Cytarabine 1.0 g/m^2 IV approximately over 24 hours daily on day 9-12 (age <60 years) or days 9-11 (age ≥ 60 years).
 
Dexamethasone 10 mg IV daily for 3-4 days with cytarabine (Duration is approximately 28 days).
   |
| EVALUATION CRITERIA               | Toxicity will be evaluated using the National Cancer Institute (NCI) Version 4.0 criteria.  |
| DURATION OF STUDY PERIOD          | Patients will continue on study until death, disease progression, unacceptable toxicity, patient refusal, or withdrawal from study.   |

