### Secondary Objectives

Determine the duration of response, disease-free survival, and overall survival.

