## **XI. OUTSIDE PHYSICIAN PARTICIPATION DURING TREATMENT AND LONG-TERM FOLLOW-UP**

- MDACC Physician communication with the outside physician is required prior to the patient returning to the local physician. This will be documented in the patient record
- A letter to the local physician outlining the patient's participation in a clinical trial will request local physician agreement to supervise the patient's care (Appendix H)
- Protocol required evaluations outside MDACC will be documented by telephone, fax or e-mail. Fax and/or e-mail will be dated and signed by the MDACC physician, indicating that they have reviewed it.
- Changes in drug dose and/or schedule must be discussed with and approved by the MDACC physician investigator, or their representative prior to initiation, and will be documented in the patient record.
- A copy of the informed consent, protocol abstract, treatment schema and evaluation during treatment will be provided to the local physician.
- Documentation to be provided by the local physician will include drug administration records, progress notes, reports of protocol required laboratory and diagnostic studies and documentation of any hospitalizations.
- The home physician will be requested to report to the MDACC physician investigator all life threatening events within 24 hours of documented occurrence.
- Patients will return to MDACC every month for evaluation prior to subsequent cycles.

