- Unless otherwise noted, the electronic SAE application (eSAE) will be utilized for safety reporting to the IND Office and MDACC IRB.
- Serious adverse events will be captured from the time of the first protocol-specific intervention, until 30 days after the last dose of drug, unless the participant withdraws consent. Serious adverse events must be followed until clinical recovery is complete and laboratory tests have returned to baseline, progression of the event has stabilized, or there has been acceptable resolution of the event.
- Additionally, any serious adverse events that occur after the 30 day time period that are related to the study treatment must be reported to the IND Office. This may include the development of a secondary malignancy.

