Descriptive statistical analysis will be calculated, including histograms or box-plots, proportions, range, means and standard deviations. Fisher's exact test and Wilcoxon rank test will be used in univariate analyses of categorical and continuous variables, respectively. Overall response (CR + CRp + PR) rate and its 95% confidence interval will be estimated using a binomial distribution. Overall survival and progression free survival functions will be estimated using the Kaplan-Meier method. The two-sided log-rank test will be used to examine the difference of survival functions among different groups. Toxicity will be reported by type, frequency and severity. Worst toxicity grades per patient will be tabulated for selected adverse events and laboratory measurements.

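### DFS and duration of response have no specified analysis while an unlisted, undefined PFS does; and, as written, deaths after a switch to alternative therapy may not be collected for OS

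*Combined protocol and SAP*

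**What the plan says.** **Objectives.** The synopsis and Section I give the same three secondary objectives: "Determine the duration of response, disease-free survival, and overall survival".

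**Analysis.** Section XX states: "Overall survival and progression free survival functions will be estimated using the Kaplan-Meier method". It adds a two-sided log-rank test between groups that it does not name, and a general sentence on descriptive statistics. DFS and duration of response are not mentioned there.

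**Follow-up.** Section X is headed "LONG TERM FOLLOW-UP (unless the patient has started on alternative therapy", and the long-term column of the schedule in Section XII repeats the condition. Its content is blood counts and chemistry every 2-3 months for up to 2 years. Return for disease evaluation is triggered by abnormal findings: "If the counts are abnormal and relapse is suspected". The end-of-treatment visit in Section IX has the same limit: "after the last dose of study drug), unless the patient has started on alternative therapy". The schedule has no row for survival status.

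**Other routes to a death date.** The synopsis says "Patients will continue on study until death, disease progression, unacceptable toxicity, patient refusal, or withdrawal from study". Section XV.F captures serious adverse events "until 30 days after the last dose of drug, unless the participant withdraws consent"; after that, only events related to treatment must be reported. Section XI says of local care: "The home physician will be requested to report to the MDACC physician investigator all life threatening events within 24 hours of documented occurrence". It also asks local physicians for progress notes and hospitalization records.

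**The concern.** There are two separate gaps.

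The first is a mismatch between objectives and analyses. Two stated endpoints have no method, start date, event or censoring rule, while a third that nobody listed has a method but no definition. The report could then present a PFS curve of the analyst's choosing and leave two objectives without a pre-specified answer.

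The second is data collection for OS. A Kaplan-Meier estimate needs deaths and last-known-alive dates for every patient, whatever treatment follows. Here scheduled contact ends when alternative therapy starts. If deaths after that point are not collected, patients are censored at the switch. Those who switch are unlikely to be a random sample: Section IV.A removes patients without an objective response after two cycles, and Section XIV lists progression and lack of response among the reasons for removal. Neither section mentions alternative therapy, so the link from non-response to switching is an inference. It is a plausible one, and it would make the censoring informative.

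**Working it through.** **1. Objectives set against analyses**

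| Endpoint | Stated objective | Analysis in Section XX | Start, event and censoring rules |
|---|---|---|---|
| OS | yes | Kaplan-Meier | none given |
| DFS | yes | none | none given |
| Duration of response | yes | none | none given |
| PFS | no | Kaplan-Meier | none given |

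The population for duration of response is also unsettled. The efficacy paragraph of Section XX counts marrow clearance of blasts as a response; the later estimation paragraph counts only CR, CRp and PR.

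**2. Can a death after the switch reach the database?**

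- End-of-treatment visit and long-term follow-up: no, neither applies after the switch.
- Study-period statement in the synopsis: it ends at the first of several events, so it is not survival follow-up.
- Serious adverse events: only to 30 days after the last dose, or later if treatment-related.
- Local physicians: possibly, but Section XI covers treatment and long-term follow-up and does not clearly reach patients who have switched.

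**3. The plan's own figures**

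The plan states no event count, power or precision for any time-to-event endpoint. Its only sample-size figures are for the two-stage response design. They reproduce by exact binomial enumeration (27 then 40 patients, limits 2 and 6): early termination 0.485 at 10% (stated 0.48), type I error 0.098 (limit 0.1), power 0.900 at 25% (stated 90%). This point does not touch them.

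**4. Possible size for OS, one case by hand**

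All survival and switching inputs are assumed. Take 40 patients, 25% responders (the design's target rate), 24 months, and exponential survival with medians of 4 months (non-responders) and 12 months (responders). Half of the non-responders switch at month 1.5 if still alive, responders do not switch, and switching does not alter survival. No later death is found.

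- Deaths by 24 months: 30×(1 − 2^(−24/4)) + 10×(1 − 2^(−24/12)) = 29.5 + 7.5 = 37.0.
- Unobserved: 30×0.5×(2^(−1.5/4) − 2^(−24/4)) = 15×(0.771 − 0.016) = 11.3, or 31% of deaths.
- True 12-month OS: 0.75×0.125 + 0.25×0.5 = 0.219.
- Survival to month 1.5: 0.75×0.771 + 0.25×0.917 = 0.808.
- Survival from 1.5 to 12 months in those left at risk: (0.75×0.5×0.125 + 0.25×0.5) / (0.75×0.5×0.771 + 0.25×0.917) = 0.1719/0.5184 = 0.332.
- Kaplan-Meier at 12 months: 0.808×0.332 = 0.268, an error of +4.9 points.

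If half of the later deaths are found, only a quarter of non-responders are censored early. The conditional term becomes 0.1953/0.6630 = 0.295, the estimate 0.238 and the error +1.9 points. The error is upward here because only non-responders leave the risk set, which enriches it for responders.

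**5. Range over assumptions**

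The simulation used 200,000 patients per scenario and 360 scenarios, each run with none and with half of the post-switch deaths found. Responder medians were 9-12 months. Non-responder medians were equal at 3, 4 or 5 months, or differed between switchers and others (6 v 2, 8 v 2, 5 v 3, 3 v 5, 3 v 4, 2 v 5). Switching was 20, 30, 50 or 70% of non-responders, at months 1-2 or 2-3, with no responders or half of them also switching.

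| Assumptions | Later deaths found | Non-responders switching | Deaths unobserved | Error in 12-month OS (points) |
|---|---|---|---|---|
| Equal survival, no responder switching | none | 20-30% | 8.8-18.8% | +0.7 to +2.4 |
| Same | none | 50-70% | 21.9-43.8% | +2.4 to +8.8 |
| Same | half | 20-30% | 4.4-9.4% | +0.1 to +1.0 |
| Same | half | 50-70% | 10.9-21.7% | +0.4 to +2.8 |
| Whole grid | none | 20-70% | 6.7-56.1% | −9.2 to +16.8 |
| Whole grid | half | 20-70% | 3.3-28.3% | −6.8 to +5.3 |

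Sampling half-width for a 12-month OS of 22%: 1.96×√(0.22×0.78/40) = 12.8 points.

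**6. Information for DFS and response duration**

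At the 25% target rate, 0.25×40 = 10 patients contribute. With 5 of 10 event-free, the exact 95% interval is 19-81%.

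**The case against.** The alternative-therapy exception qualifies sections that contain laboratory tests, adverse-event recording and return for suspected relapse. Nothing says that survival status will not be collected. A plan that names OS as an objective and estimates it by Kaplan-Meier implies that death dates will be obtained, and a single centre may well find them in its records. Section XI supplies some local documentation. Section XVII (Protocol Administration) and the appendices could not be read and might contain the missing procedure. This stands in part: what is shown is a procedure that the readable sections do not state, not an actual loss of data.

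The size is hypothetical. Every survival and switching input is assumed, the larger errors need no later death to be found, and the full range crosses zero. This stands.

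PFS may simply have been written for DFS. That is possible, but the documents do not say so, and duration of response would still have no analysis.

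A reader might infer that relapse has no definition at all. The text does not support that: Section XIII writes out relapse only after hematologic improvement, but it adopts the International Working Group criteria by citation.

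Finally, these are secondary endpoints, and two of them would rest on about 10 patients. This limits the weight of the point but does not justify leaving stated objectives without an analysis.

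**Conclusion.** The mismatch is certain from the text: DFS and duration of response are objectives without a specified analysis, and PFS is analysed without being an objective or defined. Confidence is high.

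The OS gap is held with moderate confidence because of the sections that could not be read. Followed as written, the readable sections let deaths after a switch go uncollected, and the resulting censoring is plausibly informative. Whether the error would matter depends on how many later deaths are found by other means. In the equal-survival cases it is smaller than sampling error. Unlike sampling error, it can be avoided.

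Three stronger readings are not supported. One is that post-switch deaths will be lost; the documents are silent, which is not the same. Another is that OS will be overstated; if switchers live longer than other non-responders, censoring them pushes the estimate down. The third is that the trial's main conclusion is weakened; the two-stage decision, the 40-patient sample size and the toxicity rule do not use these endpoints.

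**What to change.** 1. **Vital status.** In Section X and the schedule, keep laboratory tests conditional. Add vital status and date of death for every treated patient, every 2-3 months until death or 2 years, regardless of later therapy, by phone or record check unless the patient declines. Define OS as first dose to death from any cause, censored at the last date known alive and not at alternative therapy.

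2. **Analyses that match the objectives.** In Section XX, replace PFS with Kaplan-Meier analyses of DFS (first CR or CRp to relapse or death) and duration of response (first response to relapse, progression or death). Use one named response set that reconciles the two lists in Section XX on marrow clearance. If PFS is wanted, define it and add it as an objective alongside these two.

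3. **Alternative therapy before relapse.** State in advance how it is handled for DFS and duration of response. If patients are censored, use the last evaluation showing no relapse, and count the scheduled blood counts as well as marrow assessments. The only fixed disease assessment is Cycle 1 Day 28, so a rule based on formal assessments alone could censor responders close to their response date. Add a sensitivity analysis that ignores the switch, noting that relapse is not systematically monitored afterwards. Label both endpoints descriptive.

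The cost is amendment wording and a small coordinator workload for at most 40 patients at one centre; the vital-status check adds no visits or procedures. One drawback remains: censoring DFS or response duration at the switch may itself be informative, which is why the sensitivity analysis is needed.

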## **XI. OUTSIDE PHYSICIAN PARTICIPATION DURING TREATMENT AND LONG-TERM FOLLOW-UP**

- MDACC Physician communication with the outside physician is required prior to the patient returning to the local physician. This will be documented in the patient record
- A letter to the local physician outlining the patient's participation in a clinical trial will request local physician agreement to supervise the patient's care (Appendix H)
- Protocol required evaluations outside MDACC will be documented by telephone, fax or e-mail. Fax and/or e-mail will be dated and signed by the MDACC physician, indicating that they have reviewed it.
- Changes in drug dose and/or schedule must be discussed with and approved by the MDACC physician investigator, or their representative prior to initiation, and will be documented in the patient record.
- A copy of the informed consent, protocol abstract, treatment schema and evaluation during treatment will be provided to the local physician.
- Documentation to be provided by the local physician will include drug administration records, progress notes, reports of protocol required laboratory and diagnostic studies and documentation of any hospitalizations.
- The home physician will be requested to report to the MDACC physician investigator all life threatening events within 24 hours of documented occurrence.
- Patients will return to MDACC every month for evaluation prior to subsequent cycles.

## XII. SCHEDULE OF ASSESSMENTS

| Procedure  | Pre treatment
(Within 7 days of start of study drug except where noted) | Cycle 1   | Cycle 2-3                    | End-of-Treatment
(30 days [+/- 5 days] after the last dose of study drug) | Long Term Follow-up
(unless the patient has started on alternative therapy) |
|--|--|---|------------------------------|--|--|
| Medical History  | X  |   |                              |  |  |
| Physical examination                      | X  |   |                              |  |  |
| ECOG assessment  | X  |   |                              |  |  |
| Hematology                                 | X  | Every 4-7 days                                      | Every 1-4 weeks              | X  | Every 2-3 months for up to 2 years                                 |
| Serum Chemistry  | X    | Once each week                          | X                | X  | Every 2-3 months for up to 2 years                               |
| Bone Marrow aspirate and/or biopsy                     | X    | Day 28 (+/- 3 days)                     |                              |  |  |
| Chest x-ray  | X    |   |                              |  |  |
| Electrocardiogram                                      | X    | Day 2 (+/-1 day) and Day 8 (+/-2 days)  |                              |  |  |
| Evaluation of cardiac ejection fraction (MUGA or ECHO) | X    |   |                              |  |  |
| Urine or blood pregnancy test                          | X    |   |                              |  |  |
| Dosing (see Study Design)                              |  | Day 1 and Day 8  (+/- 2 days)          | Day 1 and Day 8 (+/- 2 days) |  |  |
| Disease Assessment                                     |  | Day 28 (+/- 3 days)                    |                              |  |  |
| Adverse Events   | X  | Continuous  |                              |  |  |
| Concomitant Medications                                | X  | Continuous  |                              |  |  |

 To include CBC with differential platelets

 Tests can be performed by local physician.

 To include glucose, total protein, albumin, electrolytes [sodium, potassium, chloride, CO2], calcium, phosphorus, magnesium, uric acid, bilirubin (total, direct), SGPT (ALT) or SGOT (AST), alkaline phosphatase, lactate dehydrogenase, creatinine, blood urea nitrogen will be performed at least weekly.

 Creatinine, total bilirubin, electrolytes, AST and/or ALT once every week during Cycle 1, then every 2-4 weeks during Cycles 2-3.

 Within one month, to include cytogenetics, unless these tests were done within 3 months.

 And as indicated until documentation of response. Bone marrow examinations may be omitted in patients where there is clear evidence of active disease (e.g., increasing blasts in peripheral blood)

 At or within 1 month of screening

 Done at least 1 hour after completion of E7070 infusion if EKG is done on the day of the E7070 infusion day

 For women of childbearing potential within 7 days prior to day 1

 If patient is found to be CR, CRp, PR or marrow clearance of blasts, may receive up to 2 additional cycles of E7070 in combination with chemotherapy

 To include vital signs and weight

 Approximately every 28 days to 2 additional cycles

